#### 1.0 DEVICE DESCRIPTION

The Hydrus Aqueous Implant is a crescent-shaped implantable device pre-loaded onto a hand-held delivery system. The Implant is delivered into Schlemm's canal by inserting the cannula of the delivery system through the trabecular meshwork and advancing the implant through the cannula. Once the implant is in position, the central core wire of the delivery system is retracted, allowing complete detachment of the Hydrus Aqueous Implant. Upon implantation, the crescent-shaped device provides a support structure, serving to dilate and restore the natural aqueous outflow pathway through Schlemm's canal, leading to a reduction of intraocular pressure.

The Hydrus Aqueous Implant is composed of nitinol, a metal alloy composed of nearly equal parts of nickel (Ni) and titanium (Ti). Nitinol has been used extensively in a variety of implantable vascular and orthopedic devices for its proven properties of flexibility, strength and biocompatibility. As a shape memory alloy, nitinol has super elastic properties making it suitable as a support structure in Schlemm's canal. Its flexibility and small size allow delivery of the Hydrus through torturous, restrictive passages with minimal force. The Hydrus Aqueous Implant is illustrated in Figure 1, on the following page.

Figure 1: The HydrusTM Aqueous Implant

#### 2.0 STUDY OBJECTIVE AND DESIGN

The objective of this clinical trial is to compare the effectiveness of one *Hydrus* to two iStents for lowering intraocular pressure (IOP) in patients with mild-to-moderate primary open angle glaucoma (POAG), pseudoexfoliative glaucoma (PXG), or pigmentary glaucoma (PG).

This study is a prospective, multicenter, single masked, randomized, clinical trial in which a total of 160 subjects (80 per study arm) will be treated with either one Hydrus or two iStents for treatment of POAG, PXG, or PG in subjects with a phakic lens. The study will be conducted according the Declaration of Helsinki. All study subjects must sign the Informed Consent prior to initiating participation in the study.

Key inclusion criteria for this study are a diagnosis of POAG, PXG, or PG based on optic nerve neuropathy, an open angle, and elevated IOP of 23-39 mmHg in the absence of hypotensive medications. In order to address the confounding effect of medications on the IOP-reducing ability of the devices, a "wash-out" of all glaucoma medications will be conducted, and a 'diurnal' methodology will be utilized to determine the subject's eligibility. The duration of wash-out will be determined by the specific medication(s) used.

Upon successfully meeting the study inclusion/exclusion criteria, subjects will be scheduled for surgery. Randomization will take place on the day of surgery just prior to treatment. Randomization sequence will be based on pre-determined computer-generated lists.

Follow up will be continued for 2 years post-surgery, and will include assessments of the subject's IOP, ocular health, and visual acuity status. Visits will be conducted at 1, 7, 30, 180, 365, 540, and 730 days.

In the event a study subject does not respond to device therapy, hypotensive glaucoma medications may be prescribed in order to reduce IOP to a safe level, as determined by the judgment of the attending physician. Medications of the same type used prior to wash out will be re-started in this event. Re-medication will not be considered an adverse event, but will be monitored. Neither the Hydrus nor the iStent devices preclude the ability to later perform filtration surgery, in the event medications do not lower pressure adequately and more invasive therapy is required.

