#### 3.0 STUDY ENDPOINTS

The primary effectiveness endpoint for this study is the proportion subjects with IOP ≤19 mmHg *and* without the use of ocular hypotensive medications at 12 months, as measured by Goldmann tonometry.

Secondary effectiveness endpoints include:

- The proportion of subjects who are are not using ocular hypotensive medications at 12 and 24 months, as measured by Goldmann tonometry
- Mean medication use at 12 and 24 months
- The proportion subjects with IOP ≤19 mmHg *and* without the use of ocular hypotensive medications at 24 months, as measured by Goldmann tonometry

Safety endpoints include:

- Frequency of loss in BCVA of 2 lines or more at 12 and 24 months,
- Slit lamp and fundus examination findings at 12 and 24 months,
- Frequency of complications and adverse events at all follow up periods.

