# 4.2 Sample Size

The study size is based on the primary endpoint.

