#### 5.0 STUDY POPULATION

#### 5.1 Inclusion Criteria

Subjects who meet the following inclusion and exclusion criteria will be eligible for enrollment in this study. Ocular criteria relates to the study eye only.

- Male and female patients from 45 to 84 years of age.
- A diagnosis of primary open angle glaucoma (POAG), pseudoexfoliative glaucoma (PXG), or pigmentary glaucoma (PG).
- A phakic patient with BCVA of 20/30 or better.
- A pseudophakic patient who has had cataract surgery >6 months from the time of study enrollment.
- Subject is on  $\geq 2$  glaucoma medications at Screening.
- Normal angle anatomy by gonioscopy with a Shaffer angle grade of ≥III in all four quadrants.
- Optic nerve pathology characteristic of glaucoma described by at least one of the following:
  - A) Thinning, narrowing, or notching of the optic disc rim.
  - B) Diffuse optic disc cupping or asymmetric cupping.
  - C) Diffuse or localized peripapillary retinal nerve fiber layer loss.
- After glaucoma medication wash-out, a mean diurnal IOP of 23-39 mmHg by Goldmann applanation tonometry.
- The subject can safely tolerate periodic wash out of glaucoma medications.
- The subject is able to understand the requirements of the study and is willing to follow study instructions, provide written informed consent, and agree to comply with all study requirements.

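### No effectiveness endpoint or planned effectiveness analysis uses the washed-out baseline IOP; adjusting the primary comparison for it would add modest precision at almost no cost

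*Combined protocol and SAP*

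**What the plan says.** Section 2.0 states the objective as comparing one Hydrus with two iStents "for lowering intraocular pressure (IOP"). It plans "a total of 160 subjects (80 per study arm").

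Section 3.0 begins: "The primary effectiveness endpoint for this study is the proportion subjects with IOP ≤19 mmHg", combined with being off ocular hypotensive medication at 12 months. The secondary effectiveness endpoints are the same composite at 24 months, the proportion "not using ocular hypotensive medications at 12 and 24 months, as measured by Goldmann tonometry", and mean medication use at both times. None is mean IOP, change in IOP or percent reduction.

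Section 4.0 has a hypothesis about needing medication to reach 19 mmHg (4.1), a single sentence on sample size, "The study size is based on the primary endpoint" (4.2), and a descriptive safety analysis (4.3). The table of contents lists no effectiveness analysis section, and no covariate is named.

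The baseline value itself is obtained with care. Section 6.2 requires washout of 14 or 28 days by drug class. Section 6.3 takes readings at three times of day and averages them. Section 5.1 requires "a mean diurnal IOP of 23-39 mmHg by Goldmann applanation tonometry". Section 7.3 uses the qualifying baseline mean once more, defining an IOP spike as a rise of at least 10 mmHg above it more than one month after surgery. Adverse-event frequency is a safety endpoint in section 3.0.

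**The concern.** The effectiveness endpoints measure whether a fixed target is met without drugs, and how many drugs are used. They do not measure how far pressure falls, which is the stated objective. As written, the plan prespecifies no estimate of IOP reduction in either arm, so any such figure would be post hoc.

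The width of the entry range also matters. With a fixed cut-off, the fall needed for success depends heavily on where the eye starts. Section 6.3 describes separate randomization lists by site but no stratification by baseline IOP. Chance differences in baseline between arms therefore add noise to the primary result, and a prespecified adjustment would remove part of it. At stake are some power and a direct answer to the objective.

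**Working it through.** **1. Fall needed to reach the target (sections 3.0 and 5.1).**
- Entry at 23 mmHg: 23 − 19 = 4 mmHg, or 4/23 = 17%.
- Entry at 39 mmHg: 39 − 19 = 20 mmHg, or 20/39 = 51%.

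**2. The plan's own figure.** The 80 per arm cannot be reproduced, because the text available gives no responder rates, alpha or power. If detail in section 4.2 was lost when the text was extracted, that is not a fault of the plan. Assuming an absolute 20-point difference, 60% versus 80% at two-sided 0.05 and 80% power needs 82 per arm; 40% versus 60% needs 97. The effect of adjustment must therefore be judged under assumptions.

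**3. Assumed inputs (none in the documents except 80 per arm).** Unmedicated 12-month IOP has SD 4.5 mmHg and the true difference is 2 mmHg. Baseline is normal with location 26.5 and scale 3.5, truncated to 23-39 mmHg. Arm means of 19.5 and 17.5 mmHg give these success rates:
- Φ((19 − 19.5)/4.5) = 45.6%
- Φ((19 − 17.5)/4.5) = 63.1%

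**4. Unadjusted power at 80 per arm, two-sided 0.05.** The difference is 0.1748. The null standard error is √(2 × 0.543 × 0.457/80) = 0.0788, and 1.96 × 0.0788 = 0.1544. The standard error under the alternative is √((0.456 × 0.544 + 0.631 × 0.369)/80) = 0.0775. Power = Φ((0.1748 − 0.1544)/0.0775) = Φ(0.26) = 60%.

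**5. Power with baseline IOP in a logistic model.** Simulated trials, testing the treatment coefficient:

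| Baseline correlation | Unadjusted (10,000 trials) | Adjusted (10,000 trials) | Gain, points | Adjusted power in smaller sets of runs |
|---|---|---|---|---|
| 0.2 | 60.1% | 62.0% | 1.9 | 61-62% |
| 0.4 | 59.0% | 64.4% | 5.4 | 62-66% |
| 0.5 | 59.1% | 67.1% | 8.0 | 67-70% |

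With 2,000 trials the simulation error of a 60% power is √(0.6 × 0.4/2000) = 1.1 points, which is compatible with the scatter in the last column. Rounded gains are 1-2, 4-6 and 7-10 points.

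A second set of assumptions (SD 4, control mean 19, difference 1.5 or 2 mmHg) gives 1-4 points at correlations of 0.2-0.3 and 7-9 points at 0.5.

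**6. Which correlation is plausible.** Restricting entry to 23-39 mmHg lowers a correlation of 0.5 to about 0.34-0.46 across the baseline distributions tried. The middle row is then nearer the mark than the last.

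**7. Rank analysis of IOP with medicated eyes ranked worst.** If eyes above 21 mmHg are the medicated ones, power without baseline is about 75-76% at every correlation. It hardly moves with the correlation because it uses no baseline information; the gain comes from not cutting IOP at 19. With baseline adjustment it is 78%, 81% and 85% at correlations of 0.2, 0.4 and 0.5.

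The advantage depends on who is medicated. At a correlation of 0.4:
- medicated above 21 mmHg: 77%
- medicated above 19 mmHg: 74%
- medicated above 17 mmHg: 64%, against 59% for the composite
- 20% of eyes also medicated at random: 52% against 40%

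The advantage therefore runs from about 64 − 59 = 5 to 77 − 59 = 18 points.

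**8. Observed IOP, ignoring medication.** This is not a safe substitute. With SD 4 and control mean 19, if 80% of eyes above 19 mmHg are medicated and fall by 4-6 mmHg, a true 1.5 mmHg difference shows as 0.8-1.0 mmHg. Power is then 39-55%, against 46% for the cut-off.

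**The case against.** The composite endpoint is defensible. Re-medication is at the investigator's discretion (section 6.8) and Appendix 1 schedules no postoperative washout, so observed IOP at 12 months mixes device and drug effects. Requiring both IOP ≤19 mmHg and no medication deals with this directly and matches section 4.1. Unequal falls are a feature of any fixed target. This stands, and the point is not that the primary endpoint should change. It is also no argument against adjusting for a value measured before randomization.

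Randomization balances baseline IOP in expectation, and the ordinary test error already covers chance imbalance. This stands too: the cost is precision, not bias.

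The plan names no effectiveness test at all, so an unadjusted comparison is an inference. That is fair. The choice of covariate is one part of that wider gap, but it is a specific part that can be settled now.

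A reader might infer more than the documents support:
- That baseline IOP is used only for eligibility. The IOP-spike definition in section 7.3 also uses it, so the point is confined to effectiveness.
- That the trial could not say how much IOP falls. Baseline and follow-up IOP are both collected; the change can be computed but is not prespecified.
- That power in the mid-70s is available to the primary comparison through baseline adjustment. That figure belongs to a different, supportive analysis and uses no baseline information.

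**Conclusion.** The point holds for effectiveness: washed-out baseline IOP enters no effectiveness endpoint and no planned effectiveness analysis, although the objective is IOP lowering. It is probably prognostic for the primary endpoint, so omitting it gives up some precision without biasing the comparison. From a base of about 60%, the gain is roughly 1-2, 4-6 or 7-10 power points at correlations of 0.2, 0.4 and 0.5. The SD, difference and correlations are assumed, as is an otherwise unadjusted test. The gain is real but modest. The change is worth making because it costs almost nothing; the primary result is valid without it.

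**What to change.** 1. **Adjust the responder comparisons.** Prespecify that the 12-month primary comparison and its 24-month counterpart use a logistic model with treatment and washed-out mean diurnal baseline IOP (continuous). Report the standardised risk difference: the average, over all subjects analysed, of predicted success under Hydrus minus predicted success under iStents. Eligibility requires the baseline value, so no properly enrolled subject should lack it.
2. **Optional supportive analysis.** Compare 12- and 24-month IOP by baseline-adjusted ranks, with medicated eyes ranked worst. State that it does not make the primary comparison more precise. State a rule for subjects terminated early, since section 6.9 says CRFs are not completed for them.
3. **Describe the size of IOP lowering.** Report mean IOP and change by arm, taking change from the 9 AM washed-out baseline reading. Section 6.3 takes follow-up IOP once, near 9 AM, so change from the diurnal mean would mix in time of day. Label any split by medication status as descriptive only, because that status arises after randomization.

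The cost is analysis text, with one more supportive analysis if item 2 is adopted. A rank result is less intuitive than a mean difference and gives no figure in mmHg, which is why item 3 is needed. Endpoints, visits and sample size do not change.

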#### 3.0 STUDY ENDPOINTS

The primary effectiveness endpoint for this study is the proportion subjects with IOP ≤19 mmHg *and* without the use of ocular hypotensive medications at 12 months, as measured by Goldmann tonometry.

Secondary effectiveness endpoints include:

- The proportion of subjects who are are not using ocular hypotensive medications at 12 and 24 months, as measured by Goldmann tonometry
- Mean medication use at 12 and 24 months
- The proportion subjects with IOP ≤19 mmHg *and* without the use of ocular hypotensive medications at 24 months, as measured by Goldmann tonometry

Safety endpoints include:

- Frequency of loss in BCVA of 2 lines or more at 12 and 24 months,
- Slit lamp and fundus examination findings at 12 and 24 months,
- Frequency of complications and adverse events at all follow up periods.

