#### 4.0 STATISTICAL METHODS

#### 4.1 Study Hypothesis

A 20% or greater reduction in the proportion of subjects requiring ocular hypotensive medications to reach a target IOP of 19 mmHg or less is a clinically significant treatment effect.

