# 4.3 Safety Analysis

Safety data (adverse events, visual acuity measurements, perimetry, and ocular health findings based on slit lamp and fundus examinations) will be evaluated using descriptive

statistics. Frequency tabulations of safety outcomes will be performed for 1, 3, 6, 12, 18 and 24-month follow up periods. Safety analysis cohorts will be grouped by actual treatment. The study is not designed to detect differences in safety outcomes.

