### **6.3** Goldmann Tonometry Procedure

At the baseline, IOP will be assessed using diurnal Goldmann tonometry, after wash-out of hypotensive medications. In this study, 3 IOP readings will be taken during daylight hours as follows:

o Time 1: 9:00 AM (± 1 hour)

- $\circ$  Time 2: 4 hours later ( $\pm$  1 hour) than Time 1
- o Time 3: 4 hours later ( $\pm$  1 hour) than Time 2

A minimum of 2 IOP readings are to be taken at each time point. If the first two IOP values at a time point are more than 2 mm apart, then a third reading should be taken.

To calculate the mean diurnal IOP, the mean IOP value from each time point is used to calculate a grand average. In the event one or more of the time points requires a third IOP reading, then the median IOP of that time point is used for the calculation of the mean diurnal IOP.

IOP readings taken at screening and at all other follow up visits will be taken once during the visit at 9 AM  $\pm$  2 hours. A minimum of 2 IOP readings are to be taken. The mean of these readings will be used for the IOP value at that visit. If the first two IOP readings are more than 2 mm apart, then a third reading should be taken. In this case the median of the 3 values will be used as the value for the visit.

If the subject meets all criteria at the Baseline visit, he or she will be scheduled for surgery within 21 days of this visit. On the day of surgery, the subject will be randomized to either the Hydrus group or iStent group. Computer-generated randomization lists will be used, with separate randomization lists for each clinical site. The subject will not be informed of the randomization assignment and all study personnel will be instructed to maintain the "masking" of the treatment assignments.

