# 7.3 Postoperative Adverse Events

- Chronic pain in the study eye  $\geq 3$  months postoperative
- Flat anterior chamber with lens/cornea touch or with iridocorneal apposition without lens/cornea touch >1 month postoperative
- Best-corrected visual acuity loss of 2 lines (10 letters) or more on the ETDRS chart compared to baseline values, measured at or after 3 months postoperative
- Hypotony (defined as IOP <6 mmHg) at or after 1 month postoperative
- Maculopathy including hypotonic maculopathy
- PAS with device obstruction
- PAS without device obstruction
- Device migration (dislodgement or movement)
- Wound dehiscence (persistent aqueous leak or fistula formation)
- Inflammation (defined as any inflammation requiring treatment with topical, sub-Tenon's or systemic anti-inflammatory medication) lasting longer than 1 month
- Endophthalmitis
- Persistent hyphema of >2 mm present >1 week postoperative
- Corneal opacification
- Corneal decompensation
- Corneal edema persisting >1 month (mild to moderate corneal edema prior to 1 month postoperative is not considered an adverse event)
- Retinal complications (flap tears, retinal detachment, or proliferative vitreoretinopathy)
- IOP spike (elevated mean IOP ≥10 mmHg above the qualifying baseline mean IOP more than 1 month postoperative)
- Events resulting in an unplanned ocular surgical re-intervention (other than paracentesis to relieve pressure prior to 1 week postoperative)
- Phthisis
- Significant foreign body sensation at or after 3 months postoperative
- A change in C/D ratio of  $\geq 0.3$  units on slit lamp biomicroscopic examination

- A 2-point worsening to 4+ anterior chamber cells or flare at or after 3 months postoperative, not associated with a pre-existing condition
- A 2-point worsening to severe on the slit lamp examination findings (other than cells and flare) at or after 3 months postoperative not associated with a pre-existing condition
- A 2-point worsening of ocular symptoms to severe or very severe at or after 3 months postoperative not associated with a pre-existing condition

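### The success definition sets only an upper IOP limit, so an unmedicated eye below 6 mmHg at the endpoint visit is both an effectiveness success and a hypotony adverse event

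*Combined protocol and SAP*

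**What the plan says.** Section 3.0 has two parts to primary success. The pressure part reads: "The primary effectiveness endpoint for this study is the proportion subjects with IOP ≤19 mmHg". The medication part reads: "without the use of ocular hypotensive medications at 12 months, as measured by Goldmann tonometry". The last secondary effectiveness endpoint repeats both parts at 24 months. Section 4.1 describes the effect of interest in the same one-sided terms: "to reach a target IOP of 19 mmHg or less is a clinically significant treatment effect".

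Section 6.3 fixes which IOP value counts at a follow-up visit: "The mean of these readings will be used for the IOP value at that visit". A median is used when a third reading is needed. No floor is set on that value.

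Section 7.3 lists among the postoperative adverse events "Hypotony (defined as IOP <6 mmHg) at or after 1 month postoperative" and, separately, "Maculopathy including hypotonic maculopathy". Section 7.1 introduces the list as events that could reasonably be expected in this trial.

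Adverse events enter the evaluation through a separate safety endpoint in Section 3.0: "Frequency of complications and adverse events at all follow up periods". Section 4.3 makes the safety analysis descriptive and adds: "The study is not designed to detect differences in safety outcomes".

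**The concern.** The effectiveness definition and the adverse event list overlap. Very low pressure off medication satisfies the first and triggers the second, and no rule says which classification prevails for effectiveness.

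The endpoint is meant to identify eyes whose pressure is controlled without drugs. The protocol itself regards pressure below 6 mmHg, from 1 month after surgery onward, as a complication. Under the present wording that complication earns full credit on the endpoint that Section 4.2 says sizes the trial. The safety tables would show it, but they do not remove the credit. If such eyes were more common in one arm, that arm's primary result would be better partly because of a complication.

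**Working it through.** **Inputs**
- Primary success: visit IOP ≤19 mmHg and no hypotensive medication at 12 months (Section 3.0); same rule at 24 months as a secondary endpoint.
- Hypotony adverse event: IOP <6 mmHg from 1 month onward (Section 7.3).
- Arm size: 80 per arm, 160 in total (Section 2.0).
- Entry IOP after wash-out: mean diurnal 23-39 mmHg (Section 5.1).
- Hypotony rate: not in the documents. Any figure below is an assumption.

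**Step 1: do the two definitions overlap?** Every value below 6 is also at or below 19. Both endpoint visits fall after 1 month. An unmedicated eye at, say, 3 mmHg at 12 months therefore meets both definitions. Sections 3.0, 4.1, 4.3, 6.3 and 7.3 contain no clause that turns hypotony, or any other adverse event, into an effectiveness failure. The overlap is certain as a matter of logic and needs no numerical assumption.

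**Step 2: how much does one eye weigh?** 1/80 = 1.25 percentage points of the arm's success rate.

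**Step 3: how many eyes?** If 1% to 3% of eyes in an arm were unmedicated and hypotonous at the visit (assumed), that is 80 × 0.01 = 0.8 to 80 × 0.03 = 2.4 eyes. This is about 1 or 2 whole eyes, or 1.25 to 2.5 points in that arm.

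**Step 4: what happens to the comparison?** If h_H and h_I eyes are reclassified in the Hydrus and iStent arms, the difference in success changes by −(h_H − h_I)/80. It is unchanged when h_H = h_I.

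To illustrate, assume success of 40% (iStent) and 60% (Hydrus), 80 per arm and two-sided alpha 0.05. Power = Φ[(d − 1.96·√(2p̄(1−p̄)/n)) / √(p₁(1−p₁)/n + p₂(1−p₂)/n)], where d is the difference, p₁ and p₂ are the two success rates, p̄ is their mean and n = 80. With no reclassification, the two square roots are 0.0791 and 0.0775, so (0.20 − 0.1549)/0.0775 = 0.58, giving 72.0%.

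| Eyes reclassified | Difference (points) | Power |
|---|---|---|
| None | 20.00 | 72.0% |
| 1, Hydrus only | 18.75 | 66.3% |
| 2, Hydrus only | 17.50 | 60.2% |
| 1, iStent only | 21.25 | 77.2% |
| 2, iStent only | 22.50 | 81.9% |
| 1 in each arm | 20.00 | 72.0% |
| 2 in each arm | 20.00 | 72.1% |

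The sign depends on which arm has the excess, and with balance the effect vanishes.

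**The plan's own figure.** The 80 per arm cannot be reproduced, because the available text of Section 4.2 gives no alpha, sidedness, power or control rate. Several assumption sets fit it. For example, a 20-point difference from 60% with two-sided 0.05 and 80% power needs 82 per arm. The point here uses 80 only as a denominator and does not depend on how it was chosen.

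**The case against.** The strongest reply is that there is no contradiction. The plan reports benefit and harm separately. A hypotonous eye is counted as an adverse event and tabulated by actual treatment, and an eye appearing in both tables is ordinary under such a scheme. No other adverse event is made an effectiveness failure either. The 6 mmHg figure is a threshold for reporting events, not a stated definition of treatment failure. Such eyes should also be rare: entry requires at least 23 mmHg after wash-out, so an eye below 6 must have fallen by more than 23 − 6 = 17 mmHg, without medication and at that particular visit.

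Much of this stands. Hypotony is not hidden, the number is probably small, and the protocol does not say that 6 mmHg marks failure. What does not stand is the inference that nothing needs changing. Hypotony differs from most listed events because it is measured on the same scale as the endpoint: the low pressure itself is what earns the success. Descriptive safety tables leave that credit in the primary comparison.

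A reader might go further and infer that the primary comparison is biased, that one device is favoured, or that over-drainage or wound leak is being rewarded. The documents do not support this. They give no hypotony rate, no reason to expect a difference between arms, and nothing on the cause of low pressure at 12 months. A reader might also set the shift against a 20-point target. Section 4.1 speaks of a 20% reduction in subjects needing medication and does not say whether that is absolute or relative, so the 20 points used above are an assumption.

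**Conclusion.** The point holds as a gap in the endpoint definition at 12 and 24 months. An unmedicated eye below 6 mmHg at the visit is a success under Section 3.0 and an adverse event under Section 7.3, and the plan does not resolve the two.

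The size is 1.25 points per eye in the affected arm, taking all 80 as the denominator. The total is unknown and probably small. The between-arm difference moves only by the imbalance in such eyes. Hypotony that occurred earlier and resolved is outside this point, since success is judged at the visit.

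This is a cheap improvement worth making, not a flaw shown to distort the result.

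**What to change.** Before outcomes are known, reconcile Sections 3.0, 4.1 and 7.3:

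- State in Section 3.0, for the 12-month primary and the matching 24-month secondary endpoint, that an eye whose visit IOP is below the protocol's own hypotony limit (<6 mmHg) is a non-success for the effectiveness analysis. Use the visit value as Section 6.3 defines it.
- Align the target wording in Section 4.1, so that it does not remain one-sided.
- Report by arm how many eyes this rule reclassifies.
- If the sponsor prefers to keep the primary definition as it is, pre-specify the same rule as a sensitivity analysis for both visits.

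This concerns classification for analysis only and implies nothing about how such an eye is managed.

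Cost: a clause in Section 3.0, a matching edit in Section 4.1 and one line of output. No extra visit or measurement is needed, since Appendix 1 already schedules Goldmann tonometry at both visits. Success rates may fall slightly, by 1.25 points per affected eye.

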#### **6.2** Medication Wash Out

After the subject has successfully completed the preoperative screening exam, he or she will be instructed to discontinue any ocular hypotensive medications in the designated treatment eye for the appropriate washout period, as listed in Table 1, *prior to* the Baseline Exam. If upon washout, the subject experiences an IOP elevation to greater than 39 mmHg, or requires the reintroduction of hypotensive medications or a surgical intervention during the preoperative period, the subject will be treated appropriately and excluded from the study. Any subject whose IOP does not fall within 23-39 mmHg will be exited from the study.

TABLE 1 OCULAR HYPOTENSIVE MEDICATION WASHOUT PERIODS									
Carbonic Anhydrase Inhibitors									
Diamox® (Acetazolamide) – oral Rx	14 days								
Neptazane® (Methazolamide) – oral Rx	14 days								
Azopt® (Brinzolamide)	14 days								
Trusopt® (Dorzolamide Hydrochloride)	14 days								
Alpha Adrenergic Agonist									
Alphagan® (Brimonidine)	14 days								
Iopidine® (Apraclonidine Hydrochloride)	14 days								
Beta Blockers									
Betagan® (Levobunolol Hydrochloride)	28 days								
Betoptic® (Betaxalol Hydrochloride)	28 days								
OptiPranolol® (Metipranolol)	28 days								
Timoptic/Betimol® (Timolol Maleate)	28 days								
Prostaglandin Analogs									
Lumigan® (Bimatoprost)	28 days								
Travatan® (Travoprost)	28 days								
Xalatan® (Latanoprost)	28 days								
Combined Medications									
Combigan® (Brimonidine Tartrate/Timolol Maleate)	28 days								
Cosopt® (Dorzolamide Hydrochloride/ Timolol Maleate)	28 days								

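### Does the plan leave open whether medication is washed out before the 12- and 24-month visits, and so what "without the use of ocular hypotensive medications at 12 months" means?

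*Combined protocol and SAP*

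**What the plan says.** All four effectiveness endpoints in Section 3.0 depend on medication use. The primary is IOP of 19 mmHg or less "without the use of ocular hypotensive medications at 12 months". The secondaries are the proportion "not using ocular hypotensive medications at 12 and 24 months", mean medication use at the same visits, and the same composite at 24 months. None gives a drug-free interval.

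Wash-out appears in four places. Section 2.0 mentions it in the sentence on determining eligibility. Section 5.1 lists as an inclusion criterion: "The subject can safely tolerate periodic wash out of glaucoma medications". Section 6.2 tells subjects, after screening and ahead of the Baseline Exam, to "discontinue any ocular hypotensive medications in the designated treatment eye for the appropriate washout period, as listed in Table 1"; the periods there are 14 or 28 days. Section 6.3 says: "At the baseline, IOP will be assessed using diurnal Goldmann tonometry, after wash-out of hypotensive medications".

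For later visits Section 6.3 has a separate rule, "IOP readings taken at screening and at all other follow up visits will be taken once during the visit", with no mention of wash-out. Section 6.8 covers starting, switching and stopping drugs after surgery, requires a record of every change, and has a masked Medical Monitor review those records. Appendix 1 assesses ocular medication at every visit from screening to month 24.

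**The concern.** *Periodic* normally means more than once, yet only one wash-out is described. Appendix 1 seems not to help, because it has no wash-out row even for baseline. If a wash-out did precede the endpoint visits, the endpoints would mean something else. A subject controlled on drops would be a non-success under visit status, but could be a success once washed out with IOP of 19 mmHg or less.

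Even without a postoperative wash-out, the missing interval leaves a loophole. A subject who stopped a drop ten days before month 12 would count as medication-free while some drug effect might remain. At stake would be the meaning of the primary endpoint, and a choice of definition made after the data are known.

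**Working it through.** **1. Which reading does the plan support?**

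| Place | What it implies |
|---|---|
| 2.0 | One wash-out, tied to eligibility; drugs restarted later are those used before it |
| 5.1 | *Periodic* tolerance, the only hint of recurrence |
| 6.2 | Wash-out between screening and the Baseline Exam; its exit rules concern the preoperative period and the qualifying IOP range |
| 6.3 | Wash-out attached to baseline diurnal IOP; follow-up IOP has its own rule without one |
| 6.8 | Medication use to control IOP is itself an endpoint; no wash-out before any visit |
| Appendix 1 | Separate screening and baseline columns, with the wash-out between them; one column each for months 12 and 24 |

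Section 2.0 gives the timetable: "Visits will be conducted at 1, 7, 30, 180, 365, 540, and 730 days". The last scheduled visits before months 12 and 24 are days 180 and 540. No visit exists at which to start a 14- or 28-day wash-out.

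**2. Does the wash-out reading leave usable endpoints?** If every subject were washed out before the visit, the proportion not using medication would be 80/80 against 80/80, and mean use would be 0 in both arms. Section 4.1 speaks of "A 20% or greater reduction in the proportion of subjects requiring ocular hypotensive medications"; after a universal wash-out there would be no medication use at the visit from which to count such subjects. A reading that empties two listed endpoints and the stated hypothesis is not a credible alternative.

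**3. How wide is the late-stop gap under visit status?** Using nominal days from 2.0 and intervals from Table 1:

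- Month 12: 365 − 180 = 185 days; 28/185 = 15.1%, 14/185 = 7.6%.
- Month 24: 730 − 540 = 190 days; 28/190 = 14.7%, 14/190 = 7.4%.

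**4. How many late stops would matter?** Inputs from the plan: 80 per arm (2.0) and 20% (4.1). Assumed: the 20% is read as an observed 20-point difference in the composite; two-sided 5% level; pooled z test, z = (p₁ − p₂)/√(2p(1 − p)/80), where p is the pooled proportion; lower-arm success of 20% to 60%. Successes in the better arm are rescored as non-successes one at a time, with none rescored in the other arm.

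| Start | Last count with p < 0.05 | First count with p > 0.05 | Rescored |
|---|---|---|---|
| 16 v 32 | 16 v 27, p = 0.0498 | 16 v 26, p = 0.072 | 6 |
| 24 v 40 | 24 v 37, p = 0.034 | 24 v 36, p = 0.05004 | 4 |
| 32 v 48 | 32 v 45, p = 0.040 | 32 v 44, p = 0.057 | 4 |
| 40 v 56 | 40 v 53, p = 0.037 | 40 v 52, p = 0.055 | 4 |
| 48 v 64 | 48 v 60, p = 0.043 | 48 v 59, p = 0.065 | 5 |

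Fisher's exact test gives 3 or 4 over the same range.

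**5. Is that many plausible?** If stops after day 180 were spread evenly, 4 in the last 28 days imply 4/0.1514 = 26.4 stops in that arm, or 26.4/80 = 33% of it. Three would imply 3/0.1514 = 19.8, or 25%. Each late stop would fall between scheduled visits, whereas Section 6.8 describes stopping a drug when IOP allows only for the immediate postoperative period.

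**The case for a change.** The best case for a change is that the contradiction is real and cheap to remove. Section 5.1 screens for a procedure that, on the favoured reading, never recurs, and Sections 4.1 to 4.3 give no scoring rule. The stated purpose of the wash-out in 2.0, removing the confounding effect of drugs on the devices' effect, would fit a postoperative wash-out too. If one took place, and if every non-success were medicated with a share s of them at 19 mmHg or less off drug in both arms, a 20-point difference would shrink to 20 × (1 − s): 18, 15 or 10 points at s = 10%, 25% or 50%. The trial is also only single masked and long-term therapy is at the investigator's discretion, so late stops need not be even between arms. The safeguards in 6.8 govern prescribing; they do not define the endpoint.

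Part of this stands. *Periodic* is a loose word and the visit-status definition is unwritten. The rest carries less weight. The purpose in 2.0 is stated in a sentence that ends with eligibility. The shrinkage figures need a wash-out that the plan nowhere schedules, values of s that no document supplies, and no unmedicated subject above 19 mmHg. The tipping counts place every late stop in one arm and depend on the test chosen. Every medication change must be recorded and reviewed by a masked monitor, so a cluster of late stops should be visible. The case report form is not among the documents, so missing stop dates cannot be assumed.

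**Conclusion.** No change to the plan follows. Followed as written, it has one wash-out before baseline and scores medication status as recorded at the 12- and 24-month visits. That is a workable definition, and analysts would reach it unprompted because the alternative makes two secondary endpoints constant. The stray word in 5.1 is a clerical looseness in a criterion applied before randomisation, so it does not affect how any subject is scored or bias the comparison between arms.

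The late-stop gap is real but narrow: at most 28 of 185 days before month 12 and 28 of 190 before month 24. Overturning an observed 20-point difference would take 4 to 6 one-sided late stops under the pooled z test, or 3 or 4 under Fisher's test; with even spread, 3 or 4 would imply that about a quarter to a third of one arm stopped a drug after day 180. These figures rest on an assumed test, level and success rates, because the plan states none, and on nominal visit days. The true frequency of late stops is unknown, but nothing in the plan makes it likely to be large. A minimum drug-free interval or an extra sensitivity analysis would have no demonstrated gain, and would score some true responders as non-successes.
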